3.4. Study Endpoints

3.4.1. Primary Endpoint

The primary study endpoint is the proportion of treatment failure at Week 6 during the double-blind randomized withdrawal phase. Treatment failure is defined as subjects who meet the following criteria at Week 6 following randomization (V9, D155):

Change (worsening) from baseline in OHSA#1 score of 1.0 point and worsening of disease severity as assessed by a 1-point change in PGI-S.

The assessments done at the Week 16 (V6, D113) visit in the OL phase prior to randomization are considered baseline for the double-blind randomized withdrawal phase of the study. Subjects who withdraw for any reason prior to V9 (D155) or subjects who fail to provide assessment at V9 (D155) will be considered as treatment failures.

3.4.2. Secondary Endpoints

The secondary endpoints include:

- Change from baseline in OHSA#1 at Week 6 post randomization (V9, D155)
- Change from baseline in OHSA composite score at Week 6 post randomization (V9, D155)
- Change from baseline in OHDAS composite score at Week 6 post randomization (V9, D155)
- Change from baseline in PGI-S at Week 6 post randomization (V9, D155)
- Change from baseline in percent of time spent in standing position as measured by a wearable device at Week 6 post randomization (V9, D155)
- Change from baseline in average number of steps taken as measured by a wearable device at Week 6 post randomization (V9, D155)

3.4.3. Safety and Tolerability Endpoint

The safety and tolerability endpoints include:

- Physical examination
- Neurological examination
- Vital signs including ambulatory BP
- Resting ECGs
- Clinical laboratory tests, including biochemistry, hematology, urinalysis
- Concomitant medication
- AEs
- C-SSRS

3.4.4. Exploratory Endpoints

Exploratory endpoints include:

- Standing SBP during orthostatic standing test at Week 6 post randomization (V9, D155)
- Change from baseline in OHQ overall composite score at Week 6 post randomization (V9, D155)
- Change from baseline in EQ-5D-5L at Week 6 post randomization (V9, D155)
- NMSS at Week 6 post randomization (V9, D155)
- HADS at Week 6 post randomization (V9, D155)
- BSFC-s at Week 6 post randomization (V9, D155)
- PK and pharmacodynamic parameters

For subjects with PD

- Change from baseline in UPDRS at Week 6 post randomization (V9, D155)
- Change from baseline in PDQ-8 at Week 6 post randomization (V9, D155)

For subjects with MSA

- Change from baseline in UMSARS at Week 6 post randomization (V9, D155)
- Change from baseline in COMPASS-31 at Week 6 post randomization (V9, D155)

3.5. Minimization of Bias

This is a randomized withdrawal study, including an OL and a placebo controlled double-blind randomized withdrawal phases. Treatments will be assigned centrally using a randomization and trial supply management (RTSM) system.

All persons involved in this study (i.e., physicians, nurses, participants, and site monitors) will remain blinded to study treatment during the randomized withdrawal period, except in the event of a medical emergency as outlined in Section [3.5.1](#).

3.5.1. Blinding

This section is only applicable to the randomized withdrawal part of the study.

TD-9855 and placebo tablets will be of the same shape, size, and color to ensure that the blind is maintained. Also, subjects who are randomized to receive placebo will receive the equivalent number of tablets as those randomized to receive TD-9855.

A subject's treatment assignment will only be unblinded when knowledge of the treatment is essential for the further clinical management of the subject on this study. Unblinding at the study site for any other reason will be considered a protocol deviation. In case of an emergency, the Investigator has the sole responsibility for determining if unblinding of a subject's treatment assignment is warranted. Subject safety must always be the first consideration in making such a determination. Any Investigator unblinding will be documented within the appropriate case report form (CRF) and will be captured in the RTSM system.

Sponsor Drug Safety personnel may independently unblind cases for expedited reporting of suspected unexpected serious adverse reactions (SUSARs). With these exceptions, sponsor personnel involved in the conduct of the study, data cleaning, or data analysis will remain blinded to subject treatment assignments until the database has been locked for final analysis.

3.5.2. Treatment Assignment

Once the subject has been determined to be eligible to receive study treatment in the OL part of the study, the PI or their delegate will use the RTSM system to provide TD-9855 to the subject and dispense study medication accordingly.

Once the subject has been determined to be eligible to receive study treatment in the randomized withdrawal part of the study, the PI or their delegate will use the RTSM system to randomize the subject and dispense study medication accordingly. Except for cases of emergency unblinding as described above, investigational site staff will remain blinded to treatment assignments until all subjects have completed the study and the database has been locked.

Further details regarding the randomization procedure and dose assignment will be outlined in the RTSM system manual.

3.5.3. Enrollment Steering Committee (for De Novo Group only)

The Investigator must obtain approval from the ESC prior to randomizing the subject in the study. The ESC is a committee of independent neurologists that will make a predetermination of the subject's appropriateness for study inclusion by reviewing medical information provided by the site. The ESC will review both the medical history to support the diagnosis (MSA, PD, or PAF), and confirm the presence of symptomatic nOH based on the results of the tilt-table test. Review of the tilt-table test results may include confirmation that the subject maintains a sustained fall in blood pressure to a level that is consistent with cerebral hypoperfusion. The ESC will consult with the Investigator to address any outstanding questions. The ESC review is recommended to be completed within 48 hours and the Investigator will be informed in writing (e.g., by e-mail) of the decision. Following ESC approval of the subject, the Investigator will determine eligibility based upon the protocol Inclusion and Exclusion criteria for randomization. In cases where the ESC determines subject ineligibility based on tilt-table test findings that are not consistent with symptomatic neurogenic orthostatic hypotension, the decision will be accompanied by rationale. A dedicated charter has been implemented to address the mode of operations of the ESC to ensure the protection of the study integrity. The communication from the ESC, documenting review and approval of the subject, will serve as ESC documentation for inclusion into the study.

4. STUDY POPULATION

This study will enroll adult subjects with confirmed symptomatic nOH due to MSA, PD, or PAF and who meet all of the applicable inclusion criteria and none of the applicable exclusion criteria defined below.

4.1. Inclusion Criteria

A subject who meets the following applicable criteria will be eligible for study enrollment:

Inclusion Criteria (For 0169 Completers Group):

101. Completion of 4 weeks of double-blind treatment in Study 0169 (V6) and, in the opinion of the Investigator, could benefit from continued treatment with TD-9855. No minimum score of OHSA#1 is required to enter V1 of Study 0170.
102. The subject has a minimum of 80% study medication compliance in Study 0169.
103. The subject must be able to understand the nature of the study and must provide written informed consent prior to the conduct of any study procedures (including an understanding that entry to Study 0170 may result in changes occurring in the subject's current therapeutic regimen).
104. The subject must be willing to continue on treatment regardless of the possibility of randomization to either TD-9855 or PBO during the randomized withdrawal phase and must continue to meet the inclusion criteria for the preceding study (Study 0169) with the exception that tilt-table test, ESC review and approval of eligibility are not required for entry into Study 0170.

Inclusion Criteria (For De Novo Group):

1. Subject is male or female and at least 30 years old.
2. If subject is female, the subject must be non-pregnant and non-lactating. A woman of childbearing potential must have a documented negative pregnancy test at screening.

NOTE: A woman is considered to be of childbearing potential unless she is postmenopausal (amenorrhic for at least 2 years) or documented to be surgically sterile (bilateral tubal ligation or total hysterectomy). A female subject may be admitted to the study on the basis of a negative urine pregnancy test. If the urine beta human chorionic gonadotropin (bHCG) test is positive, a serum bHCG test must be performed. The pregnancy test must be confirmed negative for a subject to be eligible for this study.

3. During the study and for 30 days after receiving the last dose of the study drug, females of childbearing potential or males capable of fathering children must agree to use highly effective birth control measures (failure rate <1% when used consistently and correctly) or agree to abstain from sexual intercourse. (Refer to Section 4.3).
4. Subject must meet the diagnostic criteria of nOH, as demonstrated by a sustained reduction in BP of ≥ 20 mmHg (systolic) or ≥ 10 mmHg (diastolic) within 3 min of being tilted-up $\geq 60^\circ$ from a supine position as determined by a tilt-table test.
5. Subject must score at least a 4 on the OHSA#1 at V1.
6. For subjects with PD only: Subject has a diagnosis of PD according to the United Kingdom Parkinson's Disease Society (UKPDS) Brain Bank Criteria (1992).

7. For subjects with MSA only: Subject has a diagnosis of possible or probable MSA of the Parkinsonian subtype (MSA-P) or cerebellar subtype (MSA-C) according to The Gilman Criteria (2008).
8. For subjects with PAF only: Subject has documented impaired autonomic reflexes, including the Valsalva maneuver performed within 24 months from the date of randomization.
9. Subject has plasma NE levels ≥ 100 pg/mL after being in seated position for 30 minutes.
10. Subject is willing and able to provide signed and dated written informed consent to participate prior to initiation of any study related procedures.
11. Subject is able to communicate well with the Investigator and understand clinic staff, understands the expectations of the study and is able to comply with the study procedures, requirements, and restrictions.

4.2. Exclusion Criteria

A subject who meets any of the following applicable criteria is not eligible for study enrollment:

Exclusion Criteria (For 0169 Completers Group):

101. Subject may not be enrolled in another clinical trial (other than exiting Study 0169).
102. Subject has psychiatric, neurological, or behavioral disorders that may interfere with the ability of subjects to give informed consent or interfere with the conduct of the study.
103. Medical, laboratory, or surgical issues deemed by the Investigator to be clinically significant.
104. Uncooperative attitude or reasonable likelihood of non-compliance with the protocol.
105. Subject has a concurrent disease or condition that, in the opinion of the Investigator, would confound or interfere with study participation or evaluation of safety, tolerability, or pharmacokinetics of the study drug.

Exclusion Criteria (For De Novo Group):

1. Subject has a known systemic illness known to produce autonomic neuropathy, including, but not limited to, amyloidosis and autoimmune neuropathies. Subject has diabetes mellitus and diagnosis of PAF. Subject with diabetes mellitus and either MSA or PD, will be evaluated on a case by case basis by the medical monitor and considered ineligible unless they meet all of the following criteria:
 - a. Well controlled type-2 DM in treatment with only oral medications and diet
 - b. HgbA1C of $\leq 7.5\%$ performed during screening or up to 12 weeks before screening
 - c. No clinically evident peripheral neuropathy (e.g., normal sensory examination on peripheral extremities)
 - d. No known retinopathy (e.g., annual ophthalmic exam is sufficient)
 - e. No nephropathy (e.g., absence of albuminuria and GFR >60)

2. Subject has a known intolerance to other NRIs or serotonin norepinephrine reuptake inhibitors (SNRIs).
3. Subject currently uses concomitant antihypertensive medication for the treatment of essential hypertension.
4. Subject has used strong CYP1A2 inhibitors or inducers within 7 days or 5 half-lives, whichever is longer, prior to V1 or requires concomitant use until the follow-up visit.
5. Subject has changed dose, frequency, or type of prescribed medication for orthostatic hypotension within 7 days prior to V1.
 - Midodrine and droxidopa (if applicable) must be tapered off at least 7 days prior to V1.
6. Subject has known or suspected alcohol or substance abuse within the past 12 months (Diagnostic and Statistical Manual of Mental Disorders, Fourth Edition, Text Revision [DSM-IV-TR[®]] definition of alcohol or substance abuse).
7. Subject has a clinically unstable coronary artery disease or has had a major cardiovascular or neurological event in the past 6 months.
8. Subject has used any monoamine oxidase inhibitor (MAO-I) within 14 days prior to V1.
9. Subject has a history of untreated closed angle glaucoma, or treated closed angle glaucoma that, in the opinion of an ophthalmologist, might result in an increased risk to the subject.
10. Subject has any significant uncontrolled cardiac arrhythmia.
11. Subject has a Montreal Cognitive Assessment (MoCA) ≤ 23 .
12. Subject is unable or unwilling to complete all protocol specified procedures including questionnaires.
13. Subject had a myocardial infarction in the past 6 months or has current unstable angina.
14. Subject has known congestive heart failure (New York Heart Association [NYHA] Class 3 or 4).
15. Subject has had any malignant disease, other than carcinoma in situ of the cervix or basal cell carcinoma, within the past 2 years prior to screening.
16. Subject has a known gastrointestinal (GI) condition, which in the Investigator's judgment, may affect the absorption of study medication (e.g., ulcerative colitis, gastric bypass).
17. Subject has psychiatric, neurological, or behavioral disorders that may interfere with the ability of the subject to give informed consent or interfere with the conduct of the study.
18. Subject is currently receiving any investigational drug or has received an investigational drug within 30 days of dosing. An investigational drug is defined as drug that is not approved by a regulatory agency (e.g., Food and Drug Administration [FDA]).

19. Subject has a clinically significant abnormal laboratory finding (e.g., alanine aminotransferase [ALT] or aspartate aminotransferase [AST] >3.0 x upper limit of normal [ULN]; blood bilirubin [total] >1.5 x ULN; estimated glomerular filtration rate (eGFR) <30 mL/min/1.73 m², or any abnormal laboratory value that could interfere with safety of the subject).
20. Subject has demonstrated a history of lifetime suicidal ideation and/or suicidal behavior, as outlined by the C-SSRS (Baseline/Screening Version). Subject should be assessed by the rater for risk of suicide and the subject's appropriateness for inclusion in the study.
21. Subject has a concurrent disease or condition that, in the opinion of the Investigator, would confound or interfere with study participation or evaluation of safety, tolerability, or pharmacokinetics of the study drug.
22. Subject has known hypersensitivity to TD-9855 (amprexetine hydrochloride), or any excipients in the formulation.
23. Subject has (i) confirmed severe acute respiratory syndrome coronavirus 2 (SARS-CoV-2) documented with coronavirus disease 2019 [COVID-19] positive test result, OR (ii) is suspected of SARS-CoV-2 infection (clinical features without documented test results two weeks after resolution of symptoms and remains asymptomatic until Day 1), OR (iii) has been in close contact with a person with known (or suspected) SARS-CoV-2 infection and remains asymptomatic until Day 1.

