20. Subject has demonstrated a history of lifetime suicidal ideation and/or suicidal behavior, as outlined by the C-SSRS (Baseline/Screening Version). Subject should be assessed by the rater for risk of suicide and the subject's appropriateness for inclusion in the study.
21. Subject has a concurrent disease or condition that, in the opinion of the Investigator, would confound or interfere with study participation or evaluation of safety, tolerability, or pharmacokinetics of the study drug.
22. Subject has known hypersensitivity to TD-9855 (amprelosetine hydrochloride), or any excipients in the formulation.
23. Subject has (i) confirmed severe acute respiratory syndrome coronavirus 2 (SARS-CoV-2) documented with coronavirus disease 2019 [COVID-19] positive test result, OR (ii) is suspected of SARS-CoV-2 infection (clinical features without documented test results two weeks after resolution of symptoms and remains asymptomatic until Day 1), OR (iii) has been in close contact with a person with known (or suspected) SARS-CoV-2 infection and remains asymptomatic until Day 1.

Continuation Criteria

- At V3 (Week 4), following the initial 4-week OL treatment, subjects must demonstrate a reduction in OHSA#1 of at least 2 points compared to the baseline value, as determined in Study 0169 for subjects entering from Study 0169 and from V1 for de novo subjects, in order to continue in Study 0170.

Randomization Criteria for Double-Blind Period

201. Subject has OHSA#1 score of ≤ 7 .
202. Subject's unused OL study medications (10-mg TD-9855 tablets) are returned to site.
203. The subject has a minimum of 80% study medication compliance in OL treatment period.

PROTOCOL SYNOPSIS (CONTINUED)

204. Subjects with excessive deterioration of disease or symptoms during the OL phase and in the opinion of the Investigator, would not benefit from the continual participation in the study.

The following are prohibited or restricted during study participation as specified:

- Subjects must stop the concomitant use of strong CYP1A2 inhibitors and inducers 7 days or 5 half-lives, whichever is longer, prior to randomization. This restriction applies to concomitant medications, herbal supplements (e.g., St John's Wort), and ordinary dietary intake. Please refer to [Appendix 7](#) for a list of prohibited medications.
- Prescribed medications for OH other than fludrocortisone are prohibited

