6.5. Concomitant Medications

For the De Novo Group, subjects should not have changed dose, frequency, or type of prescribed medication for orthostatic hypotension within 7 days prior to V1/D1.

Concomitant use of antihypertensive medication for the treatment of essential hypertension is not allowed.

Subjects can continue on a stable dosing regimen of fludrocortisone if the regimen was initiated at least 7 days prior to V1/D1.

Cannabinoids usage for medical reasons is permissible at a stable dosing regimen established at least 7 days prior to V1/D1 in countries where cannabinoids are permissible.

Stable dosing regimen is defined as the same dosage and frequency on any given day.

Subjects who are smokers will be recommended to either stop smoking (cigarettes or cannabinoids in countries where cannabinoids are permissible) at least 7 days before first dose or maintain a constant smoking habit during the entire course of the study.

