6.7. Prohibitions and Restrictions

The following are prohibited or restricted during study participation as specified:

- For the De Novo Group, subjects must stop the concomitant use of strong CYP1A2 inhibitors and inducers 7 days or 5 half-lives, whichever is longer, prior to V1. This restriction applies to concomitant medications, herbal supplements (e.g., St. John's Wort), and ordinary dietary intake. Refer to [Appendix 7](#) for a list of prohibited medications.
- Prescribed medications for OH other than fludrocortisone are prohibited
- Alpha blockers are prohibited (e.g., Prazosin, Terazosin, Doxazosin, Silodosin, Alfuzosin, Tamsulosin)
- Norepinephrine reuptake inhibitors (NRIs) and serotonin and norepinephrine reuptake inhibitors (SNRIs) are prohibited
 - NRIs (e.g. atomoxetine and reboxetine) and SNRIs (e.g. duloxetine, milnacipran, levomilnacipran, venlafaxine, desvenlafaxine)

- Psychostimulants (e.g. amphetamine, dextroamphetamine, methylphenidate, pemoline) are prohibited
- Subjects will be requested to refrain from making any significant dietary changes throughout the duration of the study. During their scheduled visits, subjects should be reminded to maintain an adequate fluid intake.

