APPENDIX 5. DOSING DIARY

Protocol 0170 Dosing Diary

Subject ID: _____

Date Diary Dispensed: _____ Date Diary Returned: _____

Instructions: YOU MUST BRING THIS DIARY AND YOUR STUDY MEDICATIONS TO EVERY STUDY VISIT

- 1) Please indicate the day of the week, date, time, and any comments.
- 2) Each "Time" entry should be immediately after taking the medication.
- 3) Dosing should occur every day at approximately the same time and AM or PM should be circled
- 4) Do not use any recreational drugs or drink excessive alcohol during the study period.
- 5) Do not participate in another investigational study.
- 6) Refrain from making any significant dietary changes throughout the duration of the study.
- 7) Ensure adequate fluid intake during the scheduled visits.
- 8) Subjects who are smokers will be recommended to either stop smoking >7 days before first dose or maintain a constant smoking habit during the entire course of the study.

Day of the Week/ Date	Time	Comments (E.g.: -Reason for missed or partial dose -Significant Dietary Changes)
Day of the Week: Date:	_____:____ AM / PM	
Day of the Week: Date:	_____:____ AM / PM	
Day of the Week: Date:	_____:____ AM / PM	
Day of the Week: Date:	_____:____ AM / PM	
Day of the Week: Date:	_____:____ AM / PM	
Day of the Week: Date:	_____:____ AM / PM	
Day of the Week: Date:	_____:____ AM / PM	
Day of the Week: Date:	_____:____ AM / PM	

TO BE COMPLETED BY SITE PERSONNEL ONLY:
 I confirm that I have carefully reviewed all entries in this diary.

Signature of Reviewer: _____ Date of Review: _____
 Reviewer Print Name: _____ Reviewer Title: _____

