APPENDIX 7. PROHIBITED MEDICATIONS

The following are restricted during study participation as specified:

- Strong CYP1A2 inhibitors and inducers. This restriction applies to concomitant medications, herbal supplements, and ordinary dietary intake and include, but are not limited to the following:
 - Angelica root, St John’s Wort, ciprofloxacin, clinafloxacin, enoxacin, fluvoxamine, oltipraz, rofecoxib, zafirlukast
- Prescribed medications (e.g. droxidopa, etc.) for OH other than fludrocortisone are prohibited
- Alpha blockers are prohibited (e.g., Prazosin, Terazosin, Doxazosin, Silodosin, Alfuzosin, Tamsulosin)
- Norepinephrine reuptake inhibitors (NRIs) and serotonin and norepinephrine reuptake inhibitors (SNRIs) are prohibited
 - NRIs (e.g. atomoxetine and reboxetine) and SNRIs (e.g. duloxetine, milnacipran, levomilnacipran, venlafaxine, desvenlafaxine)
- Psychostimulants (e.g. amphetamine, dextroamphetamine, methylphenidate, pemoline) are prohibited

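### The entry bar on MAO inhibitors stops at V1; no on-study rule prohibits the class during up to 22 weeks of treatment

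*Protocol*

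**What the plan says.** **Entry.** De Novo exclusion 8 (Protocol Section 4.2, repeated in the synopsis) reads "Subject has used any monoamine oxidase inhibitor (MAO-I) within 14 days prior to V1". It says nothing about use after V1.

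**A neighbouring criterion that goes further.** Exclusion 4, on strong CYP1A2 inhibitors and inducers, bars use for a set interval "prior to V1 or requires concomitant use until the follow-up visit". The same drugs appear again in Section 6.7 and Appendix 7.

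**On study.** Section 6.5 states: "Concomitant use of antihypertensive medication for the treatment of essential hypertension is not allowed". The synopsis list and Section 6.7 open with "The following are prohibited or restricted during study participation as specified", and Appendix 7 with "The following are restricted during study participation as specified". All three cover strong CYP1A2 drugs, drugs for orthostatic hypotension ("Prescribed medications for OH other than fludrocortisone are prohibited"), alpha blockers, NRIs and SNRIs, and psychostimulants. None names MAO inhibitors.

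**0169 Completers Group.** Exclusions 101 to 105 name no drug class. Inclusion 104 carries forward the inclusion criteria of Study 0169 and does not mention its exclusions.

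**General backstop.** Section 6.4.10.2 lets the investigator prescribe supportive care and asks for judgment in avoiding drugs that could cloud the study's interpretation.

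**The concern.** The protocol treats MAO inhibitor use in the two weeks before V1 as disqualifying for a De Novo subject. First dose follows on Day 2. A subject who starts or resumes an MAO inhibitor after that breaks no named rule, and a site that follows the lists to the letter has nothing telling it to refuse.

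Section 1.2.1 describes TD-9855 as inhibiting both the norepinephrine and the serotonin transporter. The on-study lists already bar other drugs that act on those transporters (NRIs and SNRIs), so they are the natural home for a rule on MAO inhibitors. If the class matters enough to exclude a subject just before dosing, the protocol should say whether it may be taken during dosing. At present it does not.

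**Working it through.** No figure in the plan depends on this point, so the check is a reading of the rules side by side.

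**1. Where the class is named.** In the visible text of both documents, MAO inhibitors appear only in exclusion 8 (Section 4.2 and its synopsis copy) and in the protocol's abbreviation list.

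**2. Time covered.** Exclusion 8 covers the 14 days before V1. Treatment is 16 weeks open-label plus 6 weeks double-blind: 16 + 6 = 22 weeks, or 22 × 7 = 154 days. Subjects randomized to placebo take TD-9855 for the first 16 weeks only. No day of either period falls under a rule that names the class.

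**3. The rules compared.**

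| Rule | Reach | MAO inhibitors named? |
|---|---|---|
| Exclusion 8 (De Novo) | 14 days before V1 | Yes |
| Exclusion 4 (De Novo) | Before V1 and on to follow-up | No; strong CYP1A2 drugs only |
| Section 6.5 | On study | No |
| Synopsis list, Section 6.7, Appendix 7 | On study | No |
| Section 6.4.10.2 | On study | No class named |

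**4. Could another entry be read to include them?**
- Appendix 7 has open-ended wording, but it sits inside the CYP1A2 bullet and extends only that bullet.
- The orthostatic hypotension entry turns on what the drug is prescribed for. An MAO inhibitor prescribed for something else falls outside it.
- The NRI/SNRI and psychostimulant entries give examples from their own classes, with no MAO inhibitor among them.
- The Appendix 5 dosing diary tells subjects "Do not use any recreational drugs or drink excessive alcohol during the study period" and "Do not participate in another investigational study". Neither instruction reaches a prescribed MAO inhibitor.

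No listed entry supplies the missing rule.

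**5. Completers.** SAP Section 4.1 says the De Novo eligibility criteria match those of Study 0169, so completers probably met an MAO inhibitor bar on entering that study. Their V1 here is the same day as Study 0169 Day 29, so that screen would be about four weeks old. Nothing visible in this protocol keeps it in force. SAP Section 6.1 shows that some completers come from the 0169 placebo arm, and these subjects first take TD-9855 here.

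**The case against.** **The mismatch does not prove an oversight.** A reader might infer that the sponsor meant to carry exclusion 8 forward and forgot. The documents do not show that. The lists also differ in the other direction: alpha blockers, NRIs, SNRIs and psychostimulants are barred on study with no matching De Novo exclusion for use. Exclusion 1a is another entry limit on drug treatment (oral agents only for diabetes) with no on-study partner. This stands, so the point rests on the absence of a rule and not on intent.

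**There are safeguards.** Section 6.4.10.2 acts before use. Concomitant-medication review, vital signs, queries for adverse events of special interest (which include supine hypertension), stopping rules, blinded sponsor review and the IDMC act afterwards. Investigators must also have read the Investigator's Brochure, which cannot be seen here and may give guidance on the class. All this narrows the gap but does not close it. The judgment clause concerns interpretation and names no drug, and the monitoring detects use or its effects without forbidding use.

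**Completers.** It would be too strong to say that they enter unscreened. Section 4.1 of the SAP points the other way, Study 0169's on-treatment rules are not available, and exclusions 103 and 105 leave the investigator discretion. What remains, mainly, is a new or resumed prescription during the study, in either group.

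**Conclusion.** The point holds as a gap in prevention. The protocol bars MAO inhibitors immediately before treatment and is silent on them during treatment, where a listed prohibition would be the ordinary control. The case rests on the protocol's own exclusion and on the dual reuptake inhibition it describes.

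Its size cannot be stated. The documents give neither the expected number of users nor the effect of combined use. Sample size, power and the primary analysis are not affected.

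Two stronger readings should be resisted:
- **That subjects were exposed to a known dangerous combination.** The documents describe no interaction, give no reason for exclusion 8 and report no on-study use.
- **That the SAP should count MAO inhibitor use as prohibited medication.** No on-study rule prohibited it, so this would relabel permitted use after the fact. SAP Section 9.3 already summarizes concomitant medications by class and preferred name and lists them all, so any use will be visible.

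Whether a change in conduct is still possible is uncertain. SAP Section 4.4 describes randomization in the past tense, and Section 8.4.1 refers to early termination by the sponsor.

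**What to change.** If dosing is still going on:
- Add *MAO inhibitors are prohibited during study treatment* to the synopsis list, Section 6.7 and Appendix 7. Word it for both enrollment groups, because the CYP1A2 entry in Section 6.7 is addressed to the De Novo Group only.
- Extend exclusion 8, in Section 4.2 and the synopsis, with exclusion 4's clause on a need for concomitant use up to the follow-up visit.

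If dosing has ended, no change is needed; the class summary and listing in SAP Section 9.3 are enough.

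**Cost.** The drafting is one line in each of three lists and one clause in exclusion 8. De Novo subjects who took an MAO inhibitor in the 14 days before V1 are already excluded. The real burden falls on a subject who comes to need one on study and would have to discontinue, and on a completer already taking one, who would have to stop it or not enrol. Neither number is known. For completers the rule would also qualify the synopsis statement that everyone who finishes Study 0169 is eligible.
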